1.2.2 Secondary estimand(s)

Not applicable.

2 Statistical methods

This section contains information that will be used to draft CSR Section 9.7 on statistical analysis.

2.1 Data analysis general information

It is planned that the data from all centers that participate in this protocol will be combined, so that an adequate number of participants will be available for analysis.

Any data analysis carried out independently by the investigator should be submitted to Novartis before publication or presentation.

The analysis will be performed at the end of the trial, after the data for all participants are available.

Unless otherwise specified, all statistical tests will be conducted against a two-sided alternative hypothesis, employing a significance level of 0.05.

Efficacy, safety, and other data will be summarized. For continuous variables, summary statistics (mean, standard deviation, median, 25th and 75th percentiles, minimum, and maximum) at each time point and for change from baseline to each time point will be reported by treatment group. For discrete variables, frequency counts and percentages at each time point will be reported by treatment group.

Lipid Parameters Units

All tabular summaries, listings, and figures of lipid parameters will be provided in traditional units). All other laboratory parameters will be analyzed in SI units. Both traditional and SI units will be included in SDTM and ADaM datasets. The lipid parameters include the following:

1. LDL Cholesterol (mg/dL)
2. Total Cholesterol (mg/dL)
3. HDL Cholesterol (mg/dL)
4. Non-HDL Cholesterol (mg/dL)
5. VLDL Cholesterol (mg/dL)

6. Triglycerides (mg/dL)
7. Apolipoprotein B (mg/dL)
8. Lipoprotein(a) (mg/dL)

[REDACTED]

[REDACTED]

2.1.1 General definitions

Study Treatment

The following are the investigational treatments:

- Inclisiran (KJX839), 284 mg, 1.5 ml liquid in a single-use prefilled syringe (PFS) for s.c. administration plus usual care
- Usual care alone

The following treatment labels will be used for all tables, listings and figures:

- Inclisiran First
- Usual Care

Study treatment start and end date

Study treatment start date is defined as the first date when a non-zero dose of study drug is administered for the inclisiran group. If a participant, who is randomized to the Inclisiran First group, does not take any study drug then treatment start date will be the randomization date.

For the usual care alone group the study treatment start date will be the randomization date.

“Day 1” will be used to identify study treatment start date for both treatments.

Study treatment end date is defined as the treatment phase completion date recorded on the “Treatment Disposition” CRF for inclisiran participants. For the usual care alone group, the study treatment end date is the last recorded contact/participation date in the database.

Study start and end date

Study start date is defined as the first date when a non-zero dose of study drug is administered for the inclisiran group. If a participant, who is randomized to the Inclisiran First group, does not take any study drug then study start date will be the randomization date.

For the usual care alone group the study start date will be the randomization date.

Study end date is defined as the date of last recorded contact/participation date in the database.

Planned and actual treatment definitions

Table 2-1 Planned and Actual Treatment Definitions

Randomized Treatment Group	Inclisiran Use Scenario During Study (Inclisiran Use Recorded as Study Treatment or Concomitant Medication)	Planned Treatment	Actual Treatment
Inclisiran First	Received at least one dose of inclisiran	Inclisiran First	Inclisiran First
Inclisiran First	Never received inclisiran	Inclisiran First	Usual Care
Usual Care	Received at least one dose of inclisiran	Usual Care	Inclisiran First
Usual Care	Never received inclisiran	Usual Care	Usual Care

Study day

Study day will be calculated as (event date – study treatment start date + 1 day) for events that occurred on or after study treatment start date (e.g., visit, lab samples, AEs). For events prior to study treatment start date (e.g., time of diagnosis), study day will be negative and calculated as (event date – study treatment start date). Note that study treatment start date is study Day 1 and the day before study treatment start date is study Day -1 (i.e., no study Day 0).

Baseline and post-baseline definitions

In general, a baseline value refers to the last measurement available prior to administration of the first dose of study treatment (before or on study Day 1). A post-baseline value refers to a measurement taken after the first dose of study treatment (after study Day 1).

Lost to follow up

Participants whose study completion status is unclear because they fail to appear for study visits without stating an intention to withdraw.

On-treatment period

The period where the participants are exposed to the study treatment or usual care. For this study the planned treatment phase consists of 330 days.

Study Completer

Completers are defined as a participant who has a Subject Status of ‘completed’ on the Study Completion/Exit CRF page.

Analysis Visit Windows

The following analysis windows will be used for efficacy and safety analyses.

Table 2-2 Analysis Visit for Each Scheduled Visit

Analysis Visit	Target Study Day*	Analysis Window	
		From	To
Baseline	1		Before randomization/First Study Treatment
Day 90	91	1	135
Day 180	181	136	225
Day 270	271	226	300
Day 330	331	301	375

* Study Day 1 is being used to identify study treatment start date. When calculating study day, the target study day will correspond to the planned study day of the nominal visit. The analysis visit values (Baseline, Day 90, Day 180, Day 270, and Day 330) will be used for all presentations.

Data collected at scheduled or unscheduled visits will be used in the analysis if they fall into an analysis window for an analysis visit. If more than one visit (scheduled or unscheduled) is made within the window specified above for any analysis visit, the non-missing assessment closest to the target study day will be used in the analysis for that visit. In the case of tied visits, non-missing data from the later visit will be used. In the case of identical collection dates and times, the average of the two visits will be used. However, all data will be included in the participant data listings.

Last Visit Summaries

The protocol uses the term End of Study (EOS) for Day 330. If a participant discontinues from the study early, they will have an early termination visit that is before Day 330. Using the windowing provided in [Table 2-2](#), the early termination visit will be assigned to the nearest analysis visit. Tables that summarize data by visit will include data by analysis visit (Baseline, Day 90, Day 180, Day 270, and Day 330) along with a Day 330/Last Visit which will combine data from Day 330 for those participants who have data collected within the Day 330 analysis window with the data from the last post-baseline visit for those participants who do not have data collected in the Day 330 analysis window.

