#### 6.1.4 Treatment duration

The planned duration of treatment is 330 days from date of randomization. Participants may be discontinued from treatment at any time due to adverse events, disease progression and/or treatment is discontinued at the discretion of the investigator or the participant.

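### Study day, baseline and windows run from first dose in the inclisiran arm but from randomization in usual care, so a first dose about 31 or more days late can leave Day 330 LDL-C missing in one arm only

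*SAP*

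**What the plan says.** SAP 2.1.1 sets the time origin by arm and by whether a dose was given:

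- Inclisiran-first, dosed: "Study treatment start date is defined as the first date when a non-zero dose of study drug is administered for the inclisiran group".
- Inclisiran-first, never dosed: if the participant "does not take any study drug then treatment start date will be the randomization date".
- Usual care: "For the usual care alone group the study treatment start date will be the randomization date".

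The study start date, which feeds study duration, carries the same split. The rest follows from these dates. "Study day will be calculated as (event date – study treatment start date + 1 day" for events on or after the start date. For baseline, "In general, a baseline value refers to the last measurement available prior to administration of the first dose of study treatment". Of Table 2-2 the SAP says "The following analysis windows will be used for efficacy and safety analyses", and data enter an analysis visit by study day, not by nominal visit. The Day 270 window is study days 226 to 300 and the Day 330 window is 301 to 375. If several values fall in one window, the one closest to the target day is used.

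SAP 2.2 analyses the Full Analysis Set as randomized. Protocol 6.1.4 counts from randomization: "The planned duration of treatment is 330 days from date of randomization". SAP section 4 records the relabelling of Day 0 as Day 1 but does not mention the arm-specific origin.

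**The concern.** In an as-randomized comparison, the clock and the baseline should be fixed by something common to both arms. Here the origin in one arm is a post-randomization event, the first injection, and in the other it is randomization. Two visits made the same number of days after randomization can therefore be assigned to different analysis visits only because of the arm. A measured primary-endpoint value can drop out of the Day 330 analysis in the inclisiran arm, while the corresponding usual-care value cannot. Late starting is also part of the strategy being tested, and the primary estimand ignores discontinuation of study treatment in order to capture the strategy as delivered. The SAP has a rule for participants who never start but none for those who start late.

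**Working it through.** **Inputs.** Let L be the number of days from randomization to first dose. A visit v days after randomization (v at least L) has study day v − L + 1 in the dosed inclisiran arm and v + 1 in usual care. Windows and targets are from SAP Table 2-2. The visit tolerance of 7 days either way is from Protocol section 8. The sampling days (screening, 0, 90, 180, 270, 330) are from SAP 1.1.

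**Plan's own figure.** With L = 0, Visit 6 has study day 330 − 0 + 1 = 331, the target in Table 2-2.

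**When Visit 6 leaves the Day 330 window.** It leaves when its study day is 300 or less.

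- On time: 331 − L ≤ 300, so L ≥ 31.
- Seven days early: 324 − L ≤ 300, so L ≥ 24.
- Seven days late: 338 − L ≤ 300, so L ≥ 38.
- Usual care: study days 324 to 338, always inside 301 to 375.

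**Which sample is then used** (visits exactly on the randomization schedule):

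| L | Visit 5 (v = 270) | Visit 6 (v = 330) | Analysed as Day 270 | Day 330 |
|---|---|---|---|---|
| 0 | 271, Day 270 | 331, Day 330 | Visit 5 | Visit 6 |
| 30 | 241, Day 270 | 301, Day 330 | Visit 5 | Visit 6 |
| 31 | 240, Day 270 | 300, Day 270 | Visit 6 (29 days from target, against 31) | missing |
| 45 | 226, Day 270 | 286, Day 270 | Visit 6 (15 against 45) | missing |
| 60 | 211, Day 180 | 271, Day 270 | Visit 6 | missing |
| 90 | 181, Day 180 | 241, Day 270 | Visit 6 | missing |

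For L = 31 to 45 the two visits share the Day 270 window and Visit 6 displaces Visit 5. From L = 46, Visit 5 itself moves to Day 180.

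**Baseline.** The value changes only if LDL-C is measured between randomization and first dose. The next scheduled sample is Day 90, at the earliest 90 − 7 = 83 days after randomization, so a scheduled sample needs a delay of about 83 days. An unscheduled or repeat sample needs much less. Protocol section 8 requires laboratory collection to be rescheduled when the participant has not fasted. A Visit 2 redraw some days after randomization, just before a delayed first dose, would be baseline in the inclisiran arm. In usual care the same redraw is post-baseline and falls in the Day 90 window.

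**Other quantities with the split origin.** Study duration (SAP 2.3.1) is the denominator for proportion of days covered (SAP 2.6.2). Restricted Set 1 (SAP 2.2) counts therapy changes only after the study treatment start date. Any delay, however short, affects these.

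**Power.** The plan's 354 reproduces: per arm 2 × (2.2414 + 1.2816)² × 40² / 15² = 176.5, rounded up to 177, and 2 × 177 = 354. With 10% loss to follow-up, 222 × 0.9 is about 200 per arm. If 0%, 1%, 5% or 10% of the inclisiran arm lost Day 330 (assumed), LDL-C power would be about 93.4%, 93.3%, 92.8% or 92%. The issue is comparability, not power.

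**The case against.** The plan leaves little room for this to happen. Randomization, kit assignment and the first injection share Visit 2 in Protocol Table 8-1, SAP 1.1 places the first dose at randomization, and neither document gives a rate of late starts. Never-dosed participants are already dated from randomization. That stands: under same-day dosing the effect is zero.

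The schedule is also not beyond doubt. SAP section 4 describes the protocol's Day 0 as the first dosing day. If sites re-timed visits from the first dose, nothing would slide under the current windows. Against this, Protocol 6.1.4 counts from randomization, and Protocol 6.5 keeps the original dosing schedule when a dose is less than 3 months late. A delay of 31 days or more with visits left in place is therefore reachable.

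Finally, the relabelled value is not discarded. It enters the MMRM as Day 270, where the unstructured covariance lets it inform the missing Day 330 value, and it appears in the Day 330/Last Visit summaries. That stands and limits the harm, but it does not restore the measured value to the visit on which the primary test is made.

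**Conclusion.** The point holds as a low-priority correction to the primary LDL-C analysis and the other windowed lipid endpoints. It rests on some first doses being given about a month or more late while visits stay on the randomization schedule or, for baseline, on an LDL-C sample being drawn between randomization and first dose. The number of such participants is unknown and probably small.

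Three stronger readings are not supported.

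- *The rule favours inclisiran.* If 1% to 3% of the arm started late and were 20 to 45 points worse at Visit 6 (all assumed), fraction times deficit gives 0.01 × 20 = 0.2 to 0.03 × 45 = 1.35 points, against a planned 15. The documents supply neither input, and they suggest little deficit. Under Protocol 6.5 a participant less than 3 months late stays on the original schedule, so the third dose still falls about 330 − 270 = 60 days before Visit 6. Protocol 4.1 puts maximum reduction at 4 to 5 months after initiation, and even a 90-day delay leaves 330 − 90 = 240 days. Because the MMRM uses the relabelled value, the product would in any case be an upper bound. With a correlation of 0.6 and equal variances (assumed), it shrinks by 1 − 0.6 = 0.4, to 0.08 to 0.54. The direction is not established.
- *Every late starter receives a post-randomization baseline.* Without an intervening LDL-C sample, the Visit 2 value remains baseline.
- *Both primary endpoints are affected.* SAP 2.5.1 sets the statin assessment date from the nominal Day 330 visit, so that date does not move.

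**What to change.** For all efficacy analyses on the Full Analysis Set, define Day 1, the analysis windows and study duration from the randomization date in both arms. Define baseline as the last value on or before that date and before any injection. Keep first-dose dating for exposure and safety. Report how many first doses came after the randomization date, and record the choice in SAP section 4.

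The cost is a wording change and one date variable. Sample size is unchanged, and results are identical where dosing is on the day of randomization. Visit 6 within tolerance of the randomization schedule then always has study day 324 to 338, whatever the dosing delay.

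Two consequences should be stated. A Visit 2 sample redrawn after randomization would no longer be baseline, so the screening value would serve in both arms. The SAP should also say that it takes visits to be counted from randomization: if a site had re-timed them from first dose, Visit 6 would have study day 331 + L and would pass 375 once L reached 45.

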### Adverse events

All information obtained on adverse events will be displayed by treatment group and participant.

The number (and percentage) of participants with treatment-emergent adverse events (events started after the first dose of study medication or events present prior to start of double-blind

treatment but increased in severity based on preferred term) will be summarized in the following ways:

- by treatment group, primary system organ class and preferred term.
- by treatment group, primary system organ class, preferred term and maximum severity.
- by treatment group, Standardized MedDRA Query (SMQ) and preferred term.

Separate summaries will be provided for study medication related adverse events, death, serious adverse events, other significant adverse events leading to discontinuation.

A participant with multiple adverse events within a primary system organ class is only counted once towards the total of the primary system organ class.

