2.7.1 Adverse events (AEs)

The Medical Dictionary for Regulatory Activities (MedDRA) dictionary will be used for coding AEs, and up-versioning will be applied during study. The final MedDRA version used in this study was v26.1. An AE (classified as preferred term) occurring during the treatment period will be counted as a treatment-emergent AE (TEAE) either if it is not present at Day 1 before treatment or if it is present before treatment but increased in severity during the treatment period.

The following summary tables will be presented:

- Overall Summary of TEAEs
- TEAEs by System Organ Class (SOC) and Preferred Term (PT)
- TEAEs by PT
- Common TEAEs ($\geq 3\%$ within either treatment group) by PT
- TEAEs by SOC, PT, and Severity
- TEAEs by SOC, PT, and Relationship to Study Treatment
- Related TEAEs by SOC, PT, and Severity
- Treatment Emergent Serious AEs (TESAEs) by SOC and PT
- TESAEs by PT
- TESAEs by SOC, PT, and Severity
- TESAEs by SOC, PT, and Relationship to Study Treatment
- Related TESAEs by SOC, PT, and Severity
- TEAEs Leading to Withdrawal of Study Treatment by SOC and PT
- TEAEs with a Fatal Outcome by SOC and PT

If more than one event occurred with the same PT for the same participant, the participant will be counted only once for that PT using the most severe or related occurrence for the summary by severity, or relationship to study drug, respectively.

Missing severity and relationship will not be imputed and will be identified as ‘missing’ in the tables.

For common (3% within either treatment group) TEAEs, serious TEAEs and TEAEs leading to withdrawal of study treatment, risk ratios along with 95% confidence intervals will be presented to compare treatment groups with respect to risk.

For tables presented by SOC and PT, system organ classes are sorted alphabetically and within each system organ class, the preferred terms are sorted in descending order of total frequency.

For tables presented by PT, preferred terms are sorted in descending order of total frequency.

Listings will be presented for participants with SAEs and AEs leading to discontinuation of study treatment.

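### The SAP counts treatment-emergent adverse events over an undefined treatment period; if its arm-specific treatment end dates bound that period, events after stopping inclisiran go uncounted while usual-care events count to last contact

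*SAP*

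**What the plan says.** SAP 2.7.1 sets the counting rule: "An AE (classified as preferred term) occurring during the treatment period will be counted as a treatment-emergent AE". The event must be absent before treatment on Day 1, or present and then worsen. The section gives no last day for the period and no number of days after the last dose.

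SAP 2.1.1 does not define a treatment period under that name. It offers two nearby definitions.

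- **Study treatment end date, by arm.** For inclisiran participants: "Study treatment end date is defined as the treatment phase completion date recorded on the" Treatment Disposition CRF. For the comparator: "For the usual care alone group, the study treatment end date is the last recorded contact/participation date in the database".
- **On-treatment period.** "The period where the participants are exposed to the study treatment or usual care", followed by "For this study the planned treatment phase consists of 330 days".

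The same section defines a study end date, and there the rule is identical in both arms: last recorded contact or participation.

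Protocol 12.5.2 takes as treatment-emergent "events started after the first dose of study medication", plus earlier events that worsen. It sets no upper limit. SAP section 4 lists six departures from the protocol, and a changed TEAE definition is not among them.

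The protocol keeps collecting the events in question. Section 8 asks participants who stop study treatment to attend the remaining visits. Section 9.1.1 makes adverse events part of the minimum data after a stop. Section 10.1.1 asks for at least 30 days of adverse event monitoring after the last dose.

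**The concern.** The planned safety comparison is a set of risk ratios with 95% confidence intervals (SAP 2.7.1). These are ratios of the proportion of participants with an event and make no adjustment for length of observation. They are fair only if both groups are counted over the same period.

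If the treatment end dates close the period, a usual-care participant counts to last contact, whereas a participant who stops inclisiran early may count only to the stop. Later events would sit in the database without entering the tables. The affected outputs would be the risk ratios for common and serious TEAEs and the special-interest tables of SAP 2.7.1.1 that are built from adverse event terms.

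The second and third doses are 180 days apart (protocol Table 6-4), so the regimen relies on a lasting effect. Closing the window at a stop with no lag would be hard to defend. It would also sit oddly beside the primary LDL-C analysis, which keeps data collected after treatment is discontinued (SAP 2.5.2).

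**Working it through.** **Step 1: which definition bounds the period?** The documents state no TEAE window length, so there is no figure to reproduce, and the question is first one of wording.

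- SAP 2.7.1 needs a start and an end for its treatment period. SAP 2.1.1 supplies a study treatment start date and a study treatment end date.
- In the visible SAP text the treatment end date has no other stated use. Duration on study (2.3.1) and proportion of days covered (2.6.1, 2.6.2) use study dates. The supplementary LDL-C analysis (2.5.6) refers to the discontinuation event, in inclisiran participants only.
- The on-treatment definition turns on exposure and gives no last day for someone who has stopped injections.

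The treatment end dates are therefore the most direct reading, but this is an inference.

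**Step 2: days lost under that reading.** With 330 planned days, a stop at day s loses (330 − s)/330:

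- Day 90: 240/330 = 73%
- Day 180: 150/330 = 45%
- Day 270: 60/330 = 18%

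A usual-care participant in contact throughout loses none.

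**Step 3: effect on the risk ratio.** Inputs from the documents: 330 days (SAP 2.1.1) and 222 participants per arm (protocol 6.1.3). Assumed inputs: true risk R over 330 days, equal in both arms, at 10% or 60%; constant hazard; a share q of the inclisiran arm stopping at day s; all stoppers otherwise followed to Day 330.

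Hazard: h = −ln(1 − R)/330.

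Reported inclisiran risk: (1 − q)R + q(1 − exp(−hs)). The risk ratio is this divided by R, and the truth is 1.00.

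Worked case, R = 0.60, q = 0.10, s = 90: h = 0.9163/330 = 0.002777; risk by Day 90 = 1 − exp(−0.2499) = 0.2211; reported risk = 0.54 + 0.0221 = 0.5621; ratio = 0.5621/0.60 = 0.937.

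| Share stopping | Stop day | Ratio, R = 10% | Ratio, R = 60% |
|---|---|---|---|
| 5% | 270 | 0.991 | 0.994 |
| 5% | 180 | 0.978 | 0.983 |
| 5% | 90 | 0.964 | 0.968 |
| 10% | 180 | 0.956 | 0.966 |
| 10% | 90 | 0.928 | 0.937 |
| 20% | 180 | 0.912 | 0.931 |
| 20% | 90 | 0.857 | 0.874 |

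**Step 4: in participants.** With R = 60% and q = 10%, the inclisiran arm would lose 222 × (0.60 − 0.5793) = 4.6 participants with a TEAE for a stop at Day 180, and 222 × (0.60 − 0.5621) = 8.4 for a stop at Day 90.

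**Step 5: with one common end date.** Both arms are counted to the same point and the expected ratio under equal hazards is 1.00.

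**The case against.** The strongest reply is that the SAP never says what this point fears. It does not tie the treatment period to the study treatment end date. Its on-treatment definition covers exposure to study treatment or usual care, and SAP 2.1.1 describes the inclisiran arm as inclisiran plus usual care. Someone who stops injections is still exposed to usual care, so on that reading nothing is cut short. Section 4 includes another departure from protocol 12.5.2 (its item on listings), so silence on TEAEs may mean that no change was intended. This stands as far as it goes: a reader might infer that the SAP expressly ends the TEAE period at discontinuation, and it does not. It leaves two workable readings that can give different counts, and the text does not choose between them.

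Other stronger readings also lack support.

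- **The inclisiran end date is the discontinuation date.** The SAP calls it a completion date. For early stoppers a discontinuation date is plausible, but the CRF is not in the documents.
- **Events vanish from one randomised arm only.** The Safety Set follows treatment received, and SAP Table 2-1 moves dosed usual-care participants into Inclisiran First and never-dosed inclisiran participants into Usual Care. Which end date they take is not stated.
- **The risk ratio for TEAEs leading to withdrawal is biased.** An event that leads to withdrawal begins before it, so this window cannot remove it.
- **Late hepatic, renal or glycaemic harm disappears altogether.** Laboratory shifts, notable values and the laboratory and medication parts of the diabetes analysis use post-baseline data without that limit. The SAE and death listings are not labelled treatment-emergent.

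The size is also open to challenge. Participants who leave the study when they stop have no later events to lose, and those who stop because of an adverse event already have one counted. Both make the model overstate the loss.

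**Conclusion.** The point holds in conditional form, with moderate confidence. It is established that the treatment period is undefined, that the treatment end dates differ by arm, that no post-dose lag is given, and that adverse events are still collected after a stop. It is inferred that the end dates bound the TEAE period. If they do, the rule departs from the open-ended protocol definition without being listed as a change, and the risk ratios for common and serious TEAEs and the AE-based special-interest tables are shifted toward inclisiran.

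The size depends on a stopping rate that the documents do not give. Under the assumptions in the working, the distortion is about 1% if few stop and stop late, 3% to 7% if 10% stop between Day 90 and Day 180, and 7% to 14% if 20% do. The last range needs heavy early stopping with full follow-up, which nothing in the documents predicts. This is a possible bias that should be closed off, and the documents do not show that it has occurred.

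**What to change.** In SAP 2.7.1, define the TEAE period for both groups as study treatment start date to study end date, meaning last recorded contact. SAP 2.1.1 already defines that end date identically for both arms. State that the same window applies to participants regrouped under Table 2-1. If an on-treatment view is also wanted, show it as a second table with its end date and any lag written out. If a restricted period is meant to remain the main definition, list it in SAP section 4 as a departure from protocol 12.5.2.

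The cost is a few lines of SAP text and one derivation flag; no new data are needed. The drawback is that some late events in participants who stopped inclisiran will be counted although unrelated to the drug. Usual-care events are counted to last contact on the same terms, so the comparison stays even.
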